Enrollment of subjects within the original study framework was put on hold beginning on March 16, 2020 due to the necessary hospital response to prevent further spread of COVID-19 and to maximize resources to treat hospitalized patients. Adding a second control group where all variables except for biologic and survey data will allow comparison of three different care conditions, intervention plus usual care, usual care only and usual care only during a pandemic. Usual care in terms of study visit timing, number, and length may be different than pre-pandemic care paradigms due to staff redeployment and restructuring are care areas to support care during a disaster.

3. Study Procedures

- a. Study design, including the sequence and timing of study procedures (distinguish research procedures from those that are part of routine care).

This pilot study uses a randomized parallel group design to determine the difference in the expression of pro- and anti-inflammatory cytokines in response to this specific exercise intervention plus usual care versus usual care only. Patients will be enrolled on day 3 of illness and data will be collected for seven consecutive days. We seek to enroll a convenience sample of up to 100 consecutive patients with supratentorial sICH and acute ischemic stroke admitted to the Johns Hopkins Hospital Neurosciences Critical Care Unit (NCCU). Patients will be screened within 24-48 hours of arrival for eligibility according to the inclusion and exclusion criteria listed below. Informed consent will be obtained from the patient or legally authorized representative (LAR). The consenting process will be performed remotely via videoconference when possible.

Patients will be randomly assigned to the intervention plus usual care or usual care only group using a standard randomization schema generated by STATA 14.0 (College Station, Texas). The AIS and sICH cohorts will have separate randomization schemas.

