arterial line is not available the non-invasive cuff will be cycled every 5 minutes. Continuous vital signs will be extracted from the Sickbay software application, which collects physiologic data on all NCCU (see IRB00132987 Multimodality Neuromonitoring in the Neurocritical Care Unit). A clinician will observe the patient at all times during the session for signs of pain and discomfort and will administer the behavioral or visual analog pain scale every 5 minutes during the session depending on the patient's level of consciousness. Patient tolerance will be defined as the absence of the following: decline in neurological examination; sustained change in intracranial pressure, blood pressure, heart rate or oxygen saturation outside of prescribed goals per established patient specific plan of care; an increase in pain as measured by the behavioral pain scale or numeric pain rating scale not easily ameliorated by position change by the clinician; and accidental tube/device/catheter removal.^{22,34} Manual muscle strength testing using the Medical Research Council Sum Score will be performed by a clinician before the first session on days three and seven for patients in the control group. General strength will be assessed using a hand-held dynamometer for patients able to follow simple commands before the first session on days three and seven for patients in the control group. Other relevant covariates will be extracted from the medical record such as delirium screening, hospital acquired infections, volume of hematoma and cerebral edema on routine CT scans and body temperature.

The second control group, retrospective observational cohort, will consist of ischemic and hemorrhagic stroke patients admitted to the NCCU on the Johns Hopkins Hospital and Johns Hopkins Bayview campuses from March 16, 2020 through the end of the prohibition of tier II and III studies declared by the Johns Hopkins University Institutional Review Board. All data collection will be accomplished through retrospective chart abstraction. Face-to-face contact will not be required. The same clinical variables will be collected for this cohort to the extent that they are recorded in the medical record from admission to 90 days after the initial ischemic or hemorrhagic stroke.

The following samples will be obtained for the intervention + usual care group and the control group, usual care only:

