- a) A 2 teaspoon sample of the patient's serum on the day of enrollment and two additional times during the seven day study period timed with routine collection of blood, when possible, for daily blood tests while the patient is in the hospital. Blood samples will be collected from an existing arterial or central line or via venipuncture. The initial blood sample will be collected on study day 1 prior to cycling in the intervention group and between 8 am-12 pm in the control group. Subsequent samples will be drawn after the second cycling session and between 2 pm and 6 pm in the control group.
- b) A 4-5 mL sample of saliva on the day of enrollment and two additional times during the seven day study period. Saliva will be collected between 8 am-10 am in all participants and prior to the first cycling session of the day for the intervention group.
- c) A 4 mL sample of cerebrospinal fluid (CSF) on the day of enrollment and two additional times during the seven day study period timed with collection of other sampling, when an external ventricular drain is in place as a part of care. CSF sampling will occur in patients with an external ventricular drain inserted as part of their care and will end after 3 samples or when the drain is discontinued. Efforts will be made to time CSF sampling with planned sampling, if possible and sampling will be performed by a nurse or physician study team member trained in the skill as part of their job using aseptic technique. The initial CSF sample will be collected on study day 1 prior to cycling in the intervention group and between 8 am-12 pm in the control group. Subsequent samples will be drawn after the second cycling session and between 2 pm and 6 pm in the control group.

All samples will be placed on dry ice, centrifuged and stored in a -70 degree Celsius freezer within 1 hour of obtaining the sample. Samples will be labeled with de-identified data (patient study number and date only).

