If a patient meets the following stopping criteria on >2 consecutive sessions the patient will be withdrawn from the study: change in neurological examination, sustained change in intracranial pressure, blood pressure, heart rate, or oxygen saturation that is outside of provider-prescribed range, significant pain exacerbated by mobilization.^{22,34}

g. Description of what happens to participants receiving therapy when study ends or if a participant's participation in the study ends prematurely.

Upon study procedure completion participants will continue to receive usual care.

4. Inclusion/Exclusion Criteria

Inclusion criteria:	Rationale:
Age \geq 18 years	Spontaneous intracerebral hemorrhage and acute ischemic stroke is typically a disease of the adult.
Supratentorial intracerebral hemorrhage with or without intraventricular hemorrhage	Only patients with a supratentorial ICH will be included due to the fact that patients with infratentorial ICH often require surgery, introducing an overlay of inflammation above that which is caused by the ICH itself. It is known that intraventricular hemorrhage increases severity of illness and mortality, however it is a common co-occurring process in patients with ICH and should be studied concurrently. ¹³
Acute ischemic stroke with a Medical Research Council Sum Score (MRCSS) of <27.	Patients with a clinical diagnosis of stroke and motor weakness as identified by the MRCSS as less than 27. ²¹
Pre-morbid modified Rankin Score of 0-2	The modified Rankin Score (mRS) is a commonly

	used tool to quantify disability after stroke and is scored from 0 to 6 with higher scores describing increased disability including death. The mRS will be used to characterize a patient's pre-morbid functional status correlating with a patient's potential for recovery after stroke as well as an outcome measure at discharge and 30 days after hemorrhage. ^{5,13} Patients with a mRS >2 prior to admission have poor potential for recovery.
Patient must be able to provide informed consent or have a legally authorized representative to provide consent on their behalf	
Exclusion criteria:	

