Patients with known inflammatory conditions, infection requiring antibiotics or pregnancy	Underlying inflammatory disorders such as, but not limited to, rheumatoid arthritis, Lupus and fibromyalgia and pregnancy will impact interpretation of inflammatory biomarkers. Patients with a diagnosed infection requiring antibiotics (e.g., bacteremia, pneumonia, urinary tract infection) at the time of screening will be excluded due to associated systemic inflammation.
Patients receiving daily anti-inflammatory medications including but not limited to prednisone, methotrexate, non-steroidal anti-inflammatory medications (ibuprofen, naproxen, indomethacin, celecoxib) and aspirin >325mg.	These anti-inflammatory medications will adversely impact our ability to interpret inflammatory markers.
Glasgow Coma Score (GCS) 3 48 hours after admission.	A GCS of 3 represents the deepest form of coma wherein no response can be elicited from the patient in terms of eye opening, verbal output and motor response. A GCS of 3 on admission portends a poor outcome. ⁴¹
Patients in whom withdrawal of life support is being considered by surrogate decision makers.	These patients are likely to die prior to or shortly after randomization. In the event that a surrogate elects not to withdraw life support, the patient will be reassessed for eligibility once more within 72 hours of the ictus.
Injury to the lower extremities, hips or pelvis, weight >250 kg (weight limit of cycle), or body habitus precluding normal function of cycle.	These injuries or physical characteristics may make the cycling activity unsafe.

5. Drugs/ Substances/ Devices

- The rationale for choosing the drug and dose or for choosing the device to be used.

The cycle ergometer (CE) is capable of facilitating movement of the upper and lower extremities regardless of the participant's ability to participate, therefore making it possible for use in patients with varying levels of consciousness and physical impairment. The CE is currently used by Rehabilitation Therapists and nurses as part of rehabilitative therapy in some NCCU patients.

- Justification and safety information if FDA approved drugs will be administered for non-FDA approved indications or if doses or routes of administration or participant populations are changed.

No medications will be administered.

c. Justification and safety information if non-FDA approved drugs without an IND will be administered.

No medications will be administered.

Study Statistics

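### Surgical inflammation is the stated reason for restricting ICH by location, but surgery is neither an eligibility criterion, a stratum nor a named covariate in the cytokine comparison

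*Combined protocol and SAP*

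**What the plan says.** Section 4 admits "Supratentorial intracerebral hemorrhage with or without intraventricular hemorrhage". The reason it gives for the location limit is that "patients with infratentorial ICH often require surgery, introducing an overlay of inflammation above that which is caused by the ICH itself". The other stroke entry criterion is "Acute ischemic stroke with a Medical Research Council Sum Score (MRCSS) of <27"; it carries no location limit and no condition on surgery.

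Section 4 also removes other sources of inflammation. It excludes "Patients with known inflammatory conditions, infection requiring antibiotics or pregnancy", and it excludes daily anti-inflammatory drugs on the ground that "These anti-inflammatory medications will adversely impact our ability to interpret inflammatory markers". The remaining exclusions are GCS 3, withdrawal of life support under consideration, and injury, weight or body habitus that prevents cycling. None of them mentions surgery.

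Section 3.a expects some patients with a neurosurgical device: "CSF sampling will occur in patients with an external ventricular drain inserted as part of their care". On data capture it says: "Other relevant covariates will be extracted from the medical record such as delirium screening, hospital acquired infections, volume of hematoma and cerebral edema", together with body temperature. Surgery is not among the examples. Randomisation is separate for AIS and sICH, with no further stratum stated. Under Study Statistics, item c, the primary comparison is a two-sample t-test on post-test values, with ANCOVA on the baseline outcome if that baseline differs. Each cohort is analysed separately with 20 per arm.

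**The concern.** The protocol names surgery as a source of inflammation over and above the stroke, and its primary outcome is five inflammatory or repair markers. It then handles surgery only through a proxy, the location of an ICH. A supratentorial ICH patient whose clot was evacuated on hospital day 1 or 2 can meet every criterion. The same is true of an AIS patient who had a decompressive operation, provided the MRCSS and general criteria are met. Such a patient's first sample, on hospital day 3, is post-operative.

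The stated aim of the pilot is to estimate an effect size. If operated patients carry different marker levels, they widen the spread of the outcome. With small arms they may also fall unevenly between the groups. Without a recorded surgery variable, a reader of the results could not tell whether that had happened.

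**Working it through.** **The plan's own figure.** For d = 0.28, 80% power and α = 0.05 (two-sided assumed), n per arm = 2(1.960 + 0.842)²/0.28² = 200.2, so 201 per arm and 402 in total. The plan states 400, and 9% of 400 is 36. The figure reproduces, and this point does not change it.

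**Where surgery could be handled.**

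| Place | Content | Surgery addressed? |
|---|---|---|
| Section 4, ICH inclusion | Supratentorial, with or without IVH | Only through location |
| Section 4, AIS inclusion | MRCSS below 27 | No |
| Section 4, exclusions | Inflammation, infection, pregnancy, drugs, GCS, withdrawal of care, cycling safety | No |
| Section 3.a, randomisation | AIS and sICH separately | No |
| Section 3.a, chart covariates | Open-ended list of examples | Not named |
| Study Statistics c | t-test; ANCOVA on baseline outcome if it differs | No |

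Study Statistics c also promises an adjusted analysis if baseline characteristics differ. It lists no characteristics, and the only adjusted model it describes is that ANCOVA.

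**Illustration of size.** The documents give neither the proportion operated (p) nor the shift in a marker caused by surgery (δ, in SDs among patients of the same surgical status). I assume p = 0.10–0.30 and δ = 0.5–1.5.

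1. *Spread.* SD factor = √(1 + p(1−p)δ²).
   - p = 0.10, δ = 0.5: √(1 + 0.09 × 0.25) = 1.011.
   - p = 0.20, δ = 1: √(1 + 0.16 × 1) = 1.077.
   - p = 0.30, δ = 1.5: √(1 + 0.21 × 2.25) = 1.213.
2. *Chance imbalance.* With X and Y independent Binomial(20, p), P(|X−Y| ≥ 3) = 0.180 at p = 0.10 and 0.387 at p = 0.30. P(|X−Y| ≥ 4) = 0.063 and 0.226.
3. *Effect of a gap.* A gap of k operated patients moves the unadjusted contrast by kδ/20. For k = 3 this is 0.075 (δ = 0.5), 0.15 (δ = 1) and 0.225 (δ = 1.5). The standard error of the contrast at 20 per arm is √(2/20) = 0.316 SD.

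Items 1 and 2–3 describe the same variation in two ways and should not be added together.

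**What baseline adjustment does.** Let surgery shift the day 1 value by δ₀ and the later value by δ₁. A gap of k then moves the change-score contrast by k(δ₁ − δ₀)/20, and an ANCOVA contrast with slope b by k(δ₁ − bδ₀)/20. A constant shift cancels in change scores, and ANCOVA reduces it to the fraction (1 − b). For example, with k = 3, δ = 1 and an assumed b = 0.5, the movement is 3 × 1 × 0.5/20 = 0.075 instead of 0.15. If the surgical component changes between study days 1 and 7, neither method removes it fully.

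**What a surgery covariate costs or gains.** With 40 patients, adjusting for one unrelated covariate inflates the variance of the contrast by about 1 + 1/36 = 1.028. Before any baseline adjustment, the ratio of adjusted to unadjusted variance is about 1.028/(1 + p(1−p)δ²):
- δ = 0: 1.028, a loss of about 3%.
- p = 0.10, δ = 0.5: 1.028/1.0225 = 1.005.
- p = 0.20, δ = 1: 1.028/1.16 = 0.886.
- p = 0.30, δ = 1.5: 1.028/1.4725 = 0.698, a gain of about 30%.

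Once the baseline cytokine is in the model, the gain is smaller.

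**The case against.** A reader might infer that the criteria contradict their own rationale. They do not. The rationale is an argument about frequency, that infratentorial ICH often needs surgery, and the criteria exclude exactly that group. The documents nowhere promise a surgery-free signal, and they knowingly admit intraventricular hemorrhage and ventricular drains. An imperfect proxy is not a contradiction. The rationale is also written for ICH only; carrying it to AIS is an extension, though a reasonable one because the outcome is the same.

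A reader might also infer that the cycling effect is biased. Randomisation rules out systematic bias from surgery before allocation, and chance imbalance is part of ordinary sampling error. Separate randomisation and analysis also mean that the AIS criterion cannot affect the sICH comparison. Setting the shifts against 0.28 overstates their importance: that effect sized a 400-patient trial, and the shift from a gap of 3 is below one standard error here.

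Some protection already exists. The first sample precedes cycling, within-participant differences are planned, and the list of chart covariates is open-ended. This protection is partial, because the named test is on post-test values and ANCOVA is conditional on a baseline difference.

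Finally, excluding operated patients may look like the natural remedy. The plan projects 3–5 patients a month over 18 months, or 54–90, for the 80 it needs. If that projection includes operated patients, removing 10–30% leaves between 54 × 0.70 ≈ 38 and 90 × 0.90 = 81. The documents do not support exclusion as a required change.

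All of these points stand. What they leave is a source of variation that the protocol itself names and makes no provision to record or use.

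**Conclusion.** The concern holds in limited form. Operated supratentorial ICH patients and, by extension, operated AIS patients can enter, and the plan neither stratifies on surgery nor names it for recording or adjustment. The consequence is added variance and possible chance imbalance in each cohort's cytokine comparison.

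The size is unknown. It runs from negligible (SD up by 1%) to material (SD up by 21%) over the assumed ranges, and it would be smaller after adjustment for the baseline cytokine. These figures rest on assumed surgery rates and shifts, on independent binomial counts, and on a shift that is the same in both arms. The gap does not invalidate the pilot, but it is worth closing because the remedy is cheap and follows from the protocol's own reasoning.

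**What to change.** Keep eligibility unchanged.

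- In Section 3.a, add to the chart variables open cranial surgery before the study day 1 sample (yes/no, type, date) and external ventricular drain status. Drains stay eligible, because the CSF objective depends on them.
- In Study Statistics c, pre-specify an ANCOVA for each cytokine in each cohort, with the baseline cytokine and pre-day-1 surgery (yes/no) as covariates whether or not the groups differ at baseline. State in advance what happens if a cohort has too few operated patients to fit the surgery term.
- Record surgery after randomisation and report it by arm, but do not adjust for it, since it could be affected by the assigned treatment.

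Cost: a few chart fields and, for surgery, one degree of freedom per model. If surgery is rare or its effect small, there is little or no gain in precision, and the loss is about 3% of variance. No patients are lost. Whether to exclude operated patients instead is a recruitment trade-off for the sponsor.

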Animal and human studies have demonstrated that moderate intensity exercise when compared to exertional exercise or strength training result in shifting of cytokine expression toward anti-inflammation and diminished markers of oxidative stress.^{7,16,24,35,45} The benefit of early exercise in AIS and sICH in decreasing pro-inflammatory factors has been demonstrated in animal models when exercise is introduced between 24 hours and three days in AIS and at three or four days in sICH.^{40,53-55} An exercise intervention that is standardized in frequency with measureable intensity and duration is necessary to explore the effects of an exercise intervention in acutely ill patients with AIS and sICH. We hypothesize that a balancing of the inflammatory response after sICH can occur with the application of moderate exercise in the acute period.

Objectives (include all primary and secondary objectives)

Primary Objective: to determine the effects of twice-daily, lower extremity CE of 20 minutes duration plus usual care, compared to usual care alone, on the trajectories of M1 versus M2 cytokine phenotypes in the serum and cerebrospinal fluid (CSF).

Secondary Objectives:

- (i) To determine the effects of twice-daily, lower extremity CE of 20 minutes duration plus usual care compared to usual care alone and a third retrospective cohort of patients receiving usual care during the COVID-19 pandemic on, the immediate and sustained physical impairment, disability scores and relevant covariates such as delirium and hospital acquired infections at NCCU discharge and 30 days after hemorrhage.
- (ii) To determine the correlation between serum and cerebrospinal fluid cytokines in patients with external CSF drainage as part of their care.
- (iii) To explore the relationship between pre-morbid physical function and quality of life and changes in inflammatory factors among all participants.
- (iv) To determine the effects of twice-daily, lower extremity CE of 20 minutes duration plus usual care alone on hemispatial neglect as measured by the Sunnybrook Neglect Assessment Procedure on day 1 of the study at transfer from the ICU or discharge from the hospital and 30 days after hemorrhage.

2. Background (briefly describe pre-clinical and clinical data, current experience with procedures, drug or device, and any other relevant information to justify the research)

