a. Primary outcome variable.

Pro-inflammatory cytokines: IL-1 β , TNF α , IL-6; Anti-inflammatory/repair factors: IL-10, BDNF

b. Secondary outcome variables will be measured at discharge and 30 days post-intracerebral hemorrhage or acute ischemic stroke.

- Modified Rankin Scale (mRS)
- Barthel Index will be measured at discharge and 30 days
- Medical Research Council Sum Score and dynamometry to measure muscle strength
- Discharge location (e.g., home, nursing facility), although not well studied, is commonly associated with physical function at discharge.
- SF-12
- Vital signs (e.g., heart, rate, blood pressure, respiratory rate)
- Delirium positive days
- Hospital acquired infections (e.g., catheter associated urinary tract infection and central line associated blood stream infection)
- CSF cytokines and repair factors
- Stroke Impact Survey

c. Statistical plan including sample size justification and interim data analysis.

Sample size was calculated for a fully powered trial and 9% of this sample size will be used for this pilot according to Cocks' methodology.¹⁰ An effect size of 0.28 was used, based on a published single group observational study in critically ill patients with a primary outcome of cytokine change.⁴⁷ Detection of an effect size of 0.28 with power of 80% and an α of 0.05 requires a sample size of 400 for a full trial and 9% represents a pilot sample size of 36 participants. Due to the enrollment of two stroke phenotypes, ischemic and hemorrhagic, we will analyze each cohort separately, therefore 40 participants per cohort are required. Accounting for attrition, up to 100 participants may be consented in order to enroll up to 40 participants per cohort. Each cohort will have 20 participants in each of two arms, intervention and control. It is estimated that at least 3-5 patients will be enrolled per month over 18 months.

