Descriptive statistics will be used to report sociodemographic variables. Baseline characteristics will be compared between the two groups. If they are found to be similar, post-intervention outcomes will be compared between the groups. If the baseline characteristics are found to be different, an adjusted analysis as described below will be conducted. Mean (SD) or median (IQR) will be used to describe continuous variables, and frequency (%) will be used for categorical variables. Mean differences in cytokines between the three time points (baseline, day 3 and day 7) will be calculated for each participant in the intervention and control groups. We will also plot data over time by group. Assumptions of normality will be checked and appropriate parametric or non-parametric tests will be used to detect absolute mean differences due to the small sample size, with an a priori significance level of 0.05, although the primary aim of this study is to estimate effect size. Data quality will be ensured by analyzing all samples in duplicate and procurement of samples will be performed by the same investigator. Statistical analysis will be performed using Stata 14.0 (College Station, Texas).

Primary aim (1): To determine whether a regimen of twice daily 20-minute sessions of CE plus usual care administered to patients with sICH and AIS (n=20) increases cytokines of the M2 phenotype and decreases cytokines of the M1 phenotype within 10 days of sICH when compared to a similar group of patients with sICH receiving usual care only (n=20).

The effect size, absolute difference between the two groups and the standard error of the difference will be estimated. The standardized difference will be estimated using Cohen's d. A two-sample t-test will be used to detect differences between post-test outcomes. If the baseline outcome is different, an analysis of covariance (ANCOVA) will be used to compare the outcomes between the two groups adjusting for the baseline difference as a covariate.

Hypothesis: Patients in the CE group will demonstrate an increase in cytokines of the M2 phenotype and a decrease in the M1 phenotype when compared to the group receiving usual care only.

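### The pilot names no lead marker or index, follow-up day or mixed-pattern rule for its five primary markers, so the effect size carried forward can be selected; CSF status also conflicts

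*Combined protocol and SAP*

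**What the plan says.** Study Statistics (a) gives the primary outcome as "Pro-inflammatory cytokines: IL-1 β , TNF α , IL-6" together with "Anti-inflammatory/repair factors: IL-10, BDNF". That makes five markers. The entry names no specimen, day, ratio or index.

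Study Statistics (c) adds three things:

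- **Time:** "Mean differences in cytokines between the three time points (baseline, day 3 and day 7) will be calculated for each participant". The two-sample t-test is then applied to post-test values without saying which day. ANCOVA is used only if the baseline differs.
- **Cohorts:** "we will analyze each cohort separately, therefore 40 participants per cohort are required", with 20 per arm in each.
- **Level:** tests are run "with an a priori significance level of 0.05, although the primary aim of this study is to estimate effect size". No adjustment for multiple comparisons is described.

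The Primary Objective asks for effects "on the trajectories of M1 versus M2 cytokine phenotypes in the serum and cerebrospinal fluid (CSF"), so it covers both fluids. Study Statistics (b) places "CSF cytokines and repair factors" among the secondary outcomes. Under Study Procedures, CSF is taken only where an external ventricular drain is in place for care, and sampling ends after three samples or when the drain comes out.

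**The concern.** The objective and the hypothesis under Primary aim (1) are about a pattern: M2 markers rise and M1 markers fall. The planned analysis compares markers one at a time. If IL-6 fell, TNF-alpha stayed flat and BDNF also fell, the plan gives no way to say whether the hypothesis was supported.

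A pilot of this kind passes an effect size to the full trial. With five markers, two follow-up days and no named lead, the team can decide after seeing the data which estimate to pass on. The largest of several noisy estimates is biased away from zero, and a trial sized on it would be too small.

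CSF adds a second ambiguity. A reader of the objective would expect a CSF result as primary, while a reader of the outcome list would not. CSF comes from a clinically selected subset that shrinks as drains are removed, so it is poorly suited to carry the primary randomised comparison.

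**Working it through.** **Inputs from the documents.** Five markers (Study Statistics a); two follow-up days, two cohorts, 20 per arm, level 0.05, planning d = 0.28, power 80%, full-trial size 400, pilot fraction 9% (Study Statistics c).

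**Assumed, because the documents give no correlations.** Correlation between markers 0.3 to 0.7; correlation between days 0.6; the correlation between different markers on different days is the product of the two. Tests are two-sided.

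**1. The plan's own figure.** n per arm = 2 × (1.96 + 0.8416)² / 0.28² = 15.70 / 0.0784 = 200.2, so 201 per arm or 402 in total. This agrees with 400, and 0.09 × 400 = 36. The sample size is not in dispute.

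**2. Number of comparisons.** 5 markers × 2 days = 10 per cohort. If only one day is tested, it is 5. Over two cohorts the range is 10 to 20.

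**3. Precision of one estimate.** The 95% half-width for d at 20 per arm is 1.96 × √(2/20 + 0.28²/80) = 1.96 × 0.318 = 0.62. A single d is already uncertain by more than twice the planning value.

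**4. Largest of 10 estimates when there is no effect.**

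- The standard error of d is about √(2/20) = 0.316.
- If the 10 are independent, the median of the largest absolute z solves P(|Z| < z)¹⁰ = 0.5. Then P(|Z| < z) = 0.5^0.1 = 0.933, z = 1.83, and the median |d| = 1.83 × 0.316 = 0.58.
- By simulation under the assumed correlations it is about 0.55 at marker correlation 0.3 and 0.48 at 0.7.
- This ignores direction. If only estimates in the hypothesised direction were eligible, the independent case becomes Φ⁻¹(0.933) × 0.316 = 1.50 × 0.316 = 0.47, which is still well above 0.28.

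**5. What that would do to the full trial.** With the formula in step 1, d = 0.48 gives 15.70 / 0.2304 = 68.1, or 69 per arm. d = 0.55 gives 15.70 / 0.3025 = 51.9, or 52 per arm. The planning value needs 201.

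**6. Chance of at least one p < 0.05 in a cohort when there is no effect.**

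| Tests per cohort | Independent | Marker correlation 0.3 | 0.5 | 0.7 |
|---|---|---|---|---|
| 10 (both days) | 1 − 0.95¹⁰ = 40% | 34% | 30% | 25% |
| 5 (one day) | 1 − 0.95⁵ = 23% | 21% | 18% | 15% |

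**7. After the change.** One named contrast gives 5% per cohort, and 1 − 0.95² = 9.75% that at least one of the two cohorts shows a false positive.

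**The case against.** The strongest reply is that this is a pilot. The sentence that sets the 0.05 level also says that estimation is the main aim, and the plan goes on to report the absolute difference, its standard error and Cohen's d. Family-wise error is a confirmatory idea, and no efficacy decision rests on these p-values. That stands, and it makes the false-positive rates in step 6 the lesser issue. It does not remove the selection problem: to carry an effect size forward, the plan has to say which one.

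A reader might infer that a chance finding is more likely than not, from 1 − 0.95²⁰ = 64%. The documents do not support that as a general statement. It requires that both days are tested, although the t-test names no day. It pools two cohorts that are randomised and analysed separately. It also requires marker correlation of about 0.5 or less: with the assumed between-day correlation, the 20-test figure is 56% at 0.3 and 43% at 0.7.

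A reader might also infer that the outcome lists themselves put CSF under both headings. They do not. The primary outcome entry names no specimen; the conflict is between the Primary Objective and the secondary list.

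Finally, a combined M1-minus-M2 index might be expected to bring a known gain in power. It cannot be quantified from the documents. If every marker shifts by 0.28 SD in the hypothesised direction, power at 20 per arm runs from about 17% (M1 and M2 correlated at −0.7) to about 93% (all markers correlated at +0.7), against 14% for one marker. The case for naming a contrast does not rest on that gain.

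**Conclusion.** The point holds as a gap in specification. The plan does not identify the marker or index, day and specimen that answer the primary question, gives no rule for a mixed pattern, and contradicts itself on whether CSF is primary.

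The main consequence is selection. Under no effect, the best-looking of 10 estimates in a cohort would typically be about 0.48 to 0.55 in absolute value, nearly twice the planning value of 0.28. The false-positive rate of about 25 to 34% per cohort (15 to 21% if one day is tested) is secondary in a pilot.

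These sizes rest on the assumed correlations, two-sided tests, 20 analysed per arm, and a choice made on size alone. They show what the plan permits; they do not show that the team intends to select. The pilot remains useful, and this is a low-cost improvement.

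**What to change.** Before any analysis:

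1. Name one primary contrast per cohort, in serum, at one follow-up time (day 7, for example), always adjusted for the baseline value by ANCOVA and not only when baselines look different.
2. Say what is contrasted. A standardised log M1-minus-M2 index is one option that fits the objective; a single lead marker is another. If the index is used, report its M1 and M2 parts beside it, because the difference can be positive when only one side moves and so does not alone show both halves of the hypothesis. Fix the weights in advance.
3. Report each marker, the other day and CSF as secondary estimates with confidence intervals.
4. Make the Primary Objective and the outcome lists agree on CSF. Keeping it secondary fits its availability only in patients with a drain.
5. If power for an index is quoted, give the range and the assumed sign of the M1-M2 correlation.

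The cost is protocol wording, with no new samples, visits or patients. The drawback is that an index can hide markers that move differently, which is why every marker stays reported.
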